## 5. TREATMENT OF SUBJECTS

NA

5.1 Investigational product/treatment

NA

5.2 Use of co-intervention (if applicable)

NA

5.3 Escape medication (if applicable)

### 6. INVESTIGATIONAL PRODUCT

6.1 Name and description of investigational product(s)

NA

6.2 Summary of findings from non-clinical studies

NA

6.3 Summary of findings from clinical studies

NA

6.4 Summary of known and potential risks and benefits

NA

6.5 Description and justification of route of administration and dosage

NA

6.6 Dosages, dosage modifications and method of administration

NA

6.7 Preparation and labelling of Investigational Medicinal Product

NA

6.8 Drug accountability

# 7. NON-INVESTIGATIONAL PRODUCT

7.1 Name and description of non-investigational product(s)

NA

7.2 Summary of findings from non-clinical studies

NA

7.3 Summary of findings from clinical studies

NA

7.4 Summary of known and potential risks and benefits

NA

7.5 Description and justification of route of administration and dosage

NA

7.6 Dosages, dosage modifications and method of administration

NA

7.7 Preparation and labelling of Non Investigational Medicinal Product

NA

7.8 Drug accountability

### 8. METHODS

### 8.1 Study parameters/endpoints

### 8.1.1 Main study parameter/endpoint

To investigate, within a dental setting, the differences between subjects with and without periodontitis:

- The prevalence of preDM and DM (established cut-off values for HbA1c, appendix 1 and 2 (7))

- The 10-year-risk of ASCVD ("10-year-risk" chart, appendix 3 (20))
- The prevalence of MetS (diagnostic criteria of NCEP ATP III, appendix 4 (21))
- The risk of OSAS (OSAS risk questionnaire (22))

### 8.1.2 Secondary study parameters/endpoints (if applicable)

- To investigate the differences in (pre)DM prevalence, 10-year-risk of ASCVD, MetS prevalence and OSAS risk between mild/moderate and severe periodontitis patients.

### 8.1.3 Other study parameters (if applicable)

- Other study parameters that will be obtained are sex, age, ethnicity (origin of parents), education level, smoking habits, diagnosis of hypertension, diagnosis of ASCVD, medical treatment for ASCVD, relatives with ASCVD, diagnosis of hypercholesterolemia, medical treatment for hypercholesterolemia, diagnosis of rheumatoid arthritis, diagnosis of DM, relatives with DM, history of periodontal treatment, height and body weight (for determining the BMI), neck and waist circumference, blood pressure, physical activity.

### 8.2 Randomisation, blinding and treatment allocation

NA

### 8.3 Study procedures

All subjects with periodontitis, diagnosed in a periodontology clinic, will be asked to participate. Subjects without periodontitis, visiting the dental school for a dental check-up, are selected and also asked to participate. The selection of subjects without periodontitis will be based on the following criteria: no interproximal alveolar bone loss on  $\leq$ 1-year-old dental bitewing radiographs, no fulfillment of criteria for the classification of periodontitis according to the Centers for Disease Control and Prevention – American Academy of Periodontology (CDC-AAP) case definition (Appendix 5) (23).

Medical information, a periodontal chart (for periodontitis patients) or a periodontal screening index (for subjects without periodontitis) and a standard dental radiographic chart will be retrieved from the patient records. During the dental appointment blood will be obtained by a finger stick. Blood analysis will be performed to acquire data on the condition of the patients.

A questionnaire about demographic characteristics will be filled in together with the periodontist or researcher, including the measurement of the systolic and diastolic blood pressure, body length and weight, waist and neck circumference. A questionnaire for assessment of the OSAS risk and a questionnaire about physical activity (IPAQ) will be asked to be filled in by the participant.

At the dental appointment, all subjects (with or without periodontitis) will undergo the following assessments during the periodontal intake or regular dental check-up:

- 1. General, medical and dental anamnesis (standard procedure)
- 2. Clinical periodontal evaluation to define the presence and severity of periodontitis (standard procedure)
- 3. Dental x-rays, when indicated for periodontitis or other dental pathology (standard procedure)
- 4. Measurement of systolic and diastolic blood pressure (standard procedure)
- 5. Measurement of length and body weight, waist and neck circumference, a questionnaire for demographic characteristics, an International Physical Activity Questionnaire (IPAQ) and an OSAS risk questionnaire. (extra procedure)
- Consecutive plasma finger stick procedure (HemCol, Labonovum B.V.) for measuring biomarkers: HbA1c, total cholesterol, LDL-C, HDL-C, triglycerides, Creactive protein (CRP), creatinine. A drop of blood is obtained with a finger stick (Greiner Bio-one Safety Lancet) and collected in a collection tube. The collection tube is sent to the laboratory for analysis by regular mail. (extra procedure)

Ad 5. The questionnaire for demographic characteristics contains a question about the ethnicity of the subject. The ethnicity is an important factor that is associated with DM and ASCVD. According to the NHG standards, the Turkish, Moroccan or Surinam-Hindustan origin is one of the risk factors for the screening of DM (24). Furthermore, it is known that ethnic differences have an influence on the HbA1c value. Factors such as differences in hemoglobin glycation, red cell survival or nonglycemic genetic determinants are being explored as determinants (25).

People of the Dutch population with a Turkish, Moroccan and Surinam-Hindustan origin have more often DM than people with a Dutch origin (26, 27). Also the prevalence of cardiovascular complications in diabetes patients is higher in people from these ethnic minorities, especially from Surinam-Hindustan. Cardiovascular diseases were more often diagnosed in people of Turkish origin compared to people of Dutch origin (28). Our study population in Amsterdam and surrounding areas has a

variety of different ethnic groups. Because ethnicity is one of the factors, related to DM and ASCVD, it has to be taken into account as a variable when measuring the biomarkers for DM and ASCVD.

All subjects will receive two letters with the result of the plasma finger stick procedure, on which the values of HbA1c, total cholesterol, LDL-C, HDL-C, triglycerides, CRP, creatinine will be reported. One letter is for the subject and the other letter is for their general practitioner (GP). The patient can decide to bring this letter to their GP. All subjects will be orally informed about their systolic and diastolic blood pressure by their dentist or researcher. When the blood values are above the known cut-off values and/or the 10-year risk of ASCVD is increased and/or the risk of OSAS is high, then the patient will be advised to visit the general practitioner for further diagnosis. An information brochure from the Thuisarts.nl, developed by the NHG, will be given when a high risk of cardiovascular diseases is suspected. Another information brochure from the The Sleep Apnea about sleep apnea will be given when the risk of OSAS is increased.

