### NL62337.029.17 / ParoSysACTA Periodontitis as signal for an underlying disease

### **10. STATISTICAL ANALYSIS**

The prevalence of (pre)DM and MetS, the 10-year risk of ASCVD and the risk of OSAS will be presented in tables. First, one table will be generated describing the background variables, blood chemistry and demographic characteristics. Secondly, the prevalence of (pre)DM and MetS, the 10-year-risk of CVD and the OSAS risk will be reported in patients with and without periodontitis.

According to the ADA guidelines HbA1c values will be classified as normal (<5.7% [<39 mmol/mol]), preDM (5.7-6.4% [39-47 mmol/mol]) and DM (≥6.5% [≥48 mmol/mol]) (7).

The 10-year risk of ASCVD will be assessed with help of the risk table from the Dutch guideline on cardiovascular risk management (CVRM) according to the standards of the Dutch College of General Practitioners (NHG) (20). The NHG standards are derived from European Society of Cardiology guidelines and modified to the Dutch situation (6).

According to the NCEP ATP III guidelines MetS is present if three of the 3 or more of the five criteria are met: elevated waist circumference over  $\geq$  102 cm (men) or  $\geq$  88 cm (women), triglyceride (TG) level over  $\geq$  1.7 mmol/L or being on drug treatment for elevated TG, high density lipoprotein cholesterol (HDL-C) level less than < 1.03 mmol/L (men) or < 1.3 mmol/L (women), blood pressure over 130/85 mmHg or on antihypertensive drug treatment, and blood glucose level over  $\geq$  5/6 mmol/L (21).

The OSAS risk is calculated with help of a new questionnaire (PhilipsQ) which is constructed from body measurements (sex, age, BMI, neck circumference) and the most predictive questions of the following OSAS and sleep questionnaires: Berlin Questionnaire (BerlinQ), STOP Questionnaire (STOPQ) and Athens Insomnia Scale (AIS). An algorithm is developed to compute the individual estimated probability (p) that a subject will have OSAS: p(OSAS) = 1 / (1+e-X), where  $X = -6.322 + 2.828 \times AIS + 2.745 \times STOPBANGQ$  High + 0.965 × STOPBANGQ Intermediate + 4.640 × BerlinQ High + 1.584 × BerlinQ Intermediate + 0.790 × Age + 0.810 × BerlinQ Q-5. The final cutoff values were determined by exploratory logistic regression analyzes. The risk of OSAS will be classified as low (p[OSAS] < 35%), intermediate (p[OSAS] = 35-55%) and high (p[OSAS] > 55%) (22).

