# **APPENDIX 1:** Criteria for the diagnosis of DM according the ADA guidelines (7)

A1C $\geq$ 6.5%. The test should be performed in a laboratory using a method that is NGSP
certified and standardized to the DCCT
assay.*
OR
FPG ≥126 mg/dL (7.0 mmol/L). Fasting is
defined as no caloric intake for at least 8 h.*
OR
2-h plasma glucose ≥200 mg/dL (11.1 mmol/L) during an OGTT. The test should be performed as described by the WHO, using a glucose load containing the equivalent of 75 g anhydrous glucose dissolved in water.* OR
In a patient with classic symptoms of hyperglycemia or hyperglycemic crisis, a random plasma glucose ≥200 mg/dL (11.1 mmol/L).

\*In the absence of unequivocal hyperglycemia, result should be confirmed by repeat testing.

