# APPENDIX 4: Criteria for diagnosis of Metabolic Syndrome (MetS) according to the NCEP ATP III (21)

Measure (any 3 of 5 constitute	Categorical cutpoints
diagnosis of metabolic syndrome)	
Elevated waist circumference (WC)	$\geq$ 102 cm in men
	$\geq$ 88 cm in women
Elevated triglycerides (TG)	$\geq$ 1.7 mmol/L
	or
	On drug treatment for elevated TG
Reduced HDL-C	< 1.03 mmol/L in men
	< 1.3 mmol/L in women
	or
	On drug treatment for reduced HDL-C
Elevated blood pressure	≥ 130 mmHg systolic blood pressure
	or
	≥ 85 mmHg diastolic blood pressure
	or
	On antihypertensive drug treatment in a
	patient with a history of hypertension
Elevated fasting glucose	$\geq$ 5.6 mmol/L

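### Fasting state is neither required nor recorded for the finger stick, so the triglyceride limb of MetS, a main endpoint, may be overstated by an unknown amount that cannot be recovered later

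*Combined protocol and SAP*

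**What the plan says.** Sections 2 and 8.1.1 name MetS prevalence among the main parameters. Section 10 and Appendix 4 score it as at least three of five limbs. Section 10 sets the triglyceride limb at or above "1.7 mmol/L or being on drug treatment for elevated TG", and Appendix 4 agrees.

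The sample is described in Section 8.3: "During the dental appointment blood will be obtained by a finger stick". The analytes begin "HbA1c, total cholesterol, LDL-C, HDL-C, triglycerides" and continue with CRP and creatinine. Plasma glucose is not on the list.

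No instruction to fast appears in Section 4, 8.3, 10 or 11.2. Section 8.1.3 ends its list with "neck and waist circumference, blood pressure, physical activity", and neither it nor Section 10.3 includes time since last intake or time of day. Fasting is mentioned only for glucose: Appendix 1, where it is "defined as no caloric intake for at least 8 h", Appendix 2, and the glucose row of Appendix 4.

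Section 10.1 says that the MetS analysis has no covariates, although the general text of Section 10 announces multiple logistic regression for primary and secondary outcomes. Fed state is in neither.

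**The concern.** Triglycerides rise after a meal. One fixed cut-off applied to people in unknown fed states therefore partly measures recent eating. The error in this limb goes one way: a meal can push someone over 1.7 mmol/L but not below it. Only people with exactly two other limbs then change MetS status.

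Two things are at stake. Section 1 says that the study should indicate the prevalence of MetS, so the absolute figure matters in its own right. The primary objective is a difference between groups, and the groups come through different routes (a referral intake and a regular check-up). If those appointments fall differently in relation to meals, part of a MetS difference could be an artefact. Since fed state is not captured, no later analysis could examine either effect.

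**Working it through.** **The plan's own figure.** The sample size concerns diabetes, not MetS. With p1 = 0.085, p2 = 0.181, mean 0.133, two-sided alpha 0.05 and 90% power:

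n = [1.960·√(2·0.133·0.867) + 1.2816·√(0.085·0.915 + 0.181·0.819)]² / 0.096² = (0.941 + 0.609)² / 0.009216 ≈ 261 per group.

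This reproduces the stated 261. The present point does not affect it.

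**Size of the triglyceride effect.** The documents give no triglyceride distribution, MetS prevalence or meal effect, so every input here is an assumption:
- fasting triglycerides log-normal, median 1.1 to 1.3 mmol/L, log-SD 0.5
- the other four limbs positive in 40%, 25%, 50% and 30%
- latent correlation between limbs 0.2 to 0.4
- everyone fed, with a rise of 10 to 40%

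Limb positivity is 1 − Φ(ln(1.7/(median × rise))/0.5). With median 1.2 and no rise, this is 1 − Φ(0.697) = 24%. With a 30% rise it is 1 − Φ(0.172) = 43%. MetS (at least three of five) was simulated in 2,000,000 subjects. The central case is median 1.2 and correlation 0.3:

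| Rise | Triglyceride limb positive | MetS |
|---|---|---|
| none | 24.3% | 27.2% |
| 10% | 30.7% | 29.0% |
| 20% | 37.0% | 30.7% |
| 30% | 43.2% | 32.4% |
| 40% | 49.1% | 34.0% |

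The central case adds 32.4 − 27.2 = 5.2 points. Over the whole grid the addition is about 1.5 to 7 points. If only a share of subjects is fed, it shrinks in proportion.

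A simpler check is added prevalence = e × f. Here e is the share with exactly two other limbs and triglycerides truly below the cut-off, and f is the share of those pushed over it. For e = 10 to 30% and f = 5 to 30%, the result is 0.5 to 9.0 points.

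**Net direction.** Leaving the limb assumed positive in 30% unscored, as may happen to glucose, central-case MetS with fed triglycerides is about 23.9%. True five-limb fasting MetS is 27.2%. The total is then about 3 points too low, although the triglyceride error still adds about 5.5 points (18.3% to 23.8%).

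**Group comparison, equal fed state.** Assume true MetS of 20% in 261 controls and 30% in 522 patients, with e = 20% in both. At f = 30% these become 26% and 36%. The difference stays at 10 points, the ratio falls from 1.50 to 0.36/0.26 = 1.38, and power falls from 86% to 81%.

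**Group comparison, unequal fed state, no true difference.**
- 80% fed in one group and 40% in the other, central case: (0.80 − 0.40) × 5.2 = 2.1 points. The standard error is about √(0.30·0.70·(1/261 + 1/522)) = 3.5 points, so the chance of a false significant result is about 9% instead of 5%.
- True MetS 25% in both, e = 20%, f = 10% against 30%: 27% against 31%, a 4-point false difference, significant in about 21 to 22% of studies.

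The documents support neither of these splits.

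**The case against.** A reader might infer that subjects are fed and that MetS prevalence is inflated in every group. The documents do not support that.
- They are silent on fasting. Subjects receive an information letter at least a week ahead (Section 11.2), and its text is not available. Consent is sought at the same visit and no study-only investigation may precede it, so a required fast is unlikely, but that is inference.
- Neither Section 10 nor Appendix 4 attaches a fasting condition to the triglyceride cut-off. The 8-hour definition in Appendix 1 belongs to plasma glucose. The direction of the triglyceride error rests on general physiology, and its size is assumed throughout.
- Net inflation of MetS is not shown, because the glucose limb has no stated source. Left unscored, it can outweigh the triglyceride effect. If HbA1c replaced it, the sign could differ.
- A reader might also infer a biased group comparison. That needs an imbalance in fed state which nothing documents.

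It can also be said that sampling at whatever time the visit falls is inherent in screening within a dental setting. That is a fair reason not to require fasting, but not a reason to leave fed state unrecorded. Even if the letter advises fasting, nothing captures whether it was followed. The gap in the plan therefore stands.

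**Conclusion.** The concern holds in a limited form. Triglycerides feed a main endpoint through one fixed cut-off, fasting is neither required nor recorded, and no planned analysis allows for it. The triglyceride limb, and through it MetS prevalence, may be overstated by an unknown amount: about 1.5 to 7 points on the assumed inputs, with the other limbs fixed and all subjects fed. The net direction for MetS as it will actually be scored is undetermined while glucose is unmeasured.

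The group difference is at risk only if fed state differs between intake patients and check-up controls, taking the share of people one limb short to be similar in both. Otherwise the main effects are a diluted ratio and a small loss of power. The change is worth making because it is cheap now and impossible after data collection.

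**What to change.** - **Data.** Add to the demographic questionnaire in Section 8.3 the hours since last caloric intake, and record the clock time of the finger stick. List both in Sections 8.1.3 and 10.3.
- **Main figure.** In Section 10.1 keep the all-subject MetS figure, labelled as based on triglycerides of unrestricted fasting state.
- **Sensitivity analyses.** Pre-specify two: (1) the MetS comparison adjusted for time since last intake; (2) the MetS comparison restricted to whole subjects above a pre-stated time since last intake or, alternatively, MetS with the triglyceride limb left out for everyone. The last version lowers prevalence by construction and serves only the group comparison.
- **Scoring.** State that the triglyceride limb will not be set to negative in fed subjects, nor treated as missing and filled by the expectation-maximization step in Section 10. Either would create a new bias linked to fed state. Triglyceride treatment counts towards the limb in Appendix 4 ("On drug treatment for elevated TG") but is missing from both parameter lists, so it needs a data source too.

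Reconcile the multiple logistic regression in Section 10 with the absence of MetS covariates in Section 10.1, so that the adjusted analysis has a clear place.

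Cost: one questionnaire item, one recorded time, two sensitivity analyses, and lower precision in the restricted one. No extra visit or procedure is needed.

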Notably, today there are several easy accessible and non-invasive techniques to screen for DM, ASCVD, MetS and OSAS. For DM there is the convenient Haemoglobin A1c (HbA1c) level, which is put forward by the American Diabetes Association (ADA) and International Diabetes Federation (IDF) as indicative of the metabolic state: prediabetes (HbA1c: 39-47 mmol/mol) and diabetes (HbA1c: ≥48 mmol/mol) (5,6). For ASCVD there is the "10-year-risk" chart, based on age, gender, total cholesterol, HDL cholesterol (HDL-C), LDL cholesterol (LDL-C), systolic and diastolic blood pressure, smoking, presence of diabetes and rheumatoid arthritis (according to the NHG standards, which are the European Society of Cardiology guidelines modified to the Dutch population)(20). The diagnostic criteria for MetS are based on waist circumference (WC), triglycerides (TG), HDL-C, hypertension and dysglycemia (according to the NCEP ATP III) (21). For OSAS there is the recently developed OSAS risk questionnaire, which scores patients into a low, moderate or high risk category of having OSAS (22).

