### NL62337.029.17 / ParoSysACTA Periodontitis as signal for an underlying disease

The majority of dental practices is not equipped for blood chemistry, however, today all plasma markers can be measured easily and accurately with help of a finger stick procedure (HemCol, Labonovum B.V., Rotterdam, The Netherlands). The measurement of the HbA1c and lipid by finger stick procedure is an elegant and essentially non-invasive way to screen for DM, ASCVD and MetS biomarkers. In addition, other demographic parameters (such as age, gender, smoking and rheumatoid arthritis) are known from the medical history and obtained with a questionnaire. Also systolic and diastolic blood pressure, Body Mass Index (BMI), Waist Circumference and N (WC) will be measured. A dental office, and in particular the dental office with a high volume of periodontitis patients, could be a suitable location for screening of individuals for early signs of DM, ASCVD, MetS and OSAS.

The importance of early identification of subjects with increased risk for DM, ASCVD and MetS lies in the prevention of DM associated micro- and macrovascular complications, future coronary heart disease and/or cerebrovascular events. Early identification in OSAS patients would result in better medical and psychological conditions. Therefore, it contributes to an increased quality of life of our patients. The results of the current study should indicate the prevalence of DM and MetS and the prevalence of patients being at increased risk for ASCVD or OSAS. This may form the basis for further studies into general applicability and cost-effectiveness.

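### Metabolic syndrome, a main endpoint, is scored with a glucose criterion, but no glucose is measured and no HbA1c substitute is written

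*Combined protocol and SAP*

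**What the plan says.** Section 8.1.1 lists among the main endpoints "The prevalence of MetS (diagnostic criteria of NCEP ATP III, appendix 4 (21"). Section 10 and Appendix 4 both require at least three of five criteria, and section 10.1 again refers MetS to the NCEP ATP III criteria. The fifth criterion is glucose. Section 10 words it as "blood glucose level over" a threshold in mmol/L and does not mention fasting. Appendix 4 has "Elevated fasting glucose" at or above 5.6 mmol/L.

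The blood panel in section 8.3 is "for measuring biomarkers: HbA1c, total cholesterol, LDL-C, HDL-C, triglycerides, Creactive protein (CRP), creatinine". The letter to the subject and the general practitioner repeats the same seven analytes: "the values of HbA1c, total cholesterol, LDL-C, HDL-C, triglycerides, CRP, creatinine will be reported".

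Two sentences in section 1 hint that HbA1c was meant to fill the gap. One reads "The diagnostic criteria for MetS are based on waist circumference (WC), triglycerides (TG), HDL-C, hypertension and dysglycemia". The other says that measuring "HbA1c and lipid by finger stick procedure is an elegant and essentially non-invasive way to screen for DM, ASCVD and MetS biomarkers". The only HbA1c cut-offs are those for the diabetes endpoint in section 10: "preDM (5.7-6.4% [39-47 mmol/mol]) and DM (≥6.5% [≥48 mmol/mol"]).

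**The concern.** The scoring rule for a main endpoint calls for a measurement that the study does not take. As written, the analyst would have to choose a glycaemic marker and cut-off, or drop the criterion, with the data already in hand.

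That choice is not neutral. A lower HbA1c cut-off raises MetS prevalence. Dropping the criterion lowers prevalence and removes whatever group difference the criterion carries, and the plan's own hypothesis is that (pre)DM is more common in periodontitis. A decision made after seeing the data could therefore move the comparison being tested.

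**Working it through.** **1. Rule against data.**

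| MetS criterion | Source in the plan |
|---|---|
| Waist circumference | Measured (8.3) |
| Triglycerides | Finger stick (8.3) |
| HDL-C | Finger stick (8.3) |
| Blood pressure | Measured (8.3) |
| Glucose | None |

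Section 8.3 also retrieves medical information from patient records, but no glucose value is planned from it.

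**2. Who cannot be classified.** Let k be the number met among the other four criteria, taken as scored.
- k = 0 or 1: at most 2 of 5, so no MetS whatever the glucose.
- k = 3 or 4: MetS whatever the glucose.
- k = 2: MetS if glucose is raised, otherwise not, so undetermined. This is C(4,2) = 6 of the 2⁴ = 16 patterns.

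**3. Imputation.** Section 10 imputes missing data by expectation-maximization. A variable with no observed value in any subject gives nothing from which to estimate its distribution, so this does not help.

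**4. The plan's own figure.** None exists for MetS. The 261 per group in section 4.4 rests on DM (8.5% v 18.1%) and reproduces with two-sided α 0.05 and 90% power: (1.960 × √(2 × 0.133 × 0.867) + 1.2816 × √(0.085 × 0.915 + 0.181 × 0.819))² / 0.096² = 260.9, so 261. It does not depend on MetS.

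**5. Size of the undetermined group (assumed inputs).** Base prevalences for waist/TG/HDL-C/blood pressure: 40/30/25/50%.
- Independent criteria: P(k = 2) = 0.0450 + 0.0350 + 0.1050 + 0.0225 + 0.0675 + 0.0525 = 0.3275, or 256 of 783. P(k ≥ 3) = 0.0150 + 0.0450 + 0.0350 + 0.0225 + 0.0150 = 0.1325. MetS prevalence is then only bounded: 13.25% to 13.25 + 32.75 = 46.0%.
- Correlated criteria: a one-factor latent-normal model with correlation ρ, in which criterion j with prevalence pⱼ has conditional probability Φ((√ρ·z − tⱼ)/√(1 − ρ)), tⱼ = Φ⁻¹(1 − pⱼ), integrated over z. At ρ = 0.4, P(k = 2) = 22.0% (172 of 783) and P(k ≥ 3) = 22.0%.
- A low set (30/20/20/40%) gives 18.1–24.1% undetermined; a high set (50/35/30/60%) gives 24.5–37.8%.

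**6. Effect of the HbA1c cut-off.** MetS = P(k ≥ 3) + P(k = 2 and glycaemic criterion met). Assume 25% or 40% at or above 39 mmol/mol, and 8.5% or 18.1% at or above 48 (pilot rates of new DM in controls and severe periodontitis). For the base set with independence:
- 25% v 8.5%: 0.3275 × (0.25 − 0.085) = 5.4% (42 of 783).
- 25% v 18.1%: 0.3275 × 0.069 = 2.3% (18).
- 40% v 8.5%: 0.3275 × 0.315 = 10.3% (81).
- 40% v 18.1%: 0.3275 × 0.219 = 7.2% (56).

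At ρ = 0.4, with HbA1c on the same factor, these become 4.6%, 1.9%, 8.7% and 6.0% (36, 15, 68, 47). Across all three component sets the ranges are 1.7–6.2% (25% at or above 39) and 5.2–11.9% (40%).

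**7. Effect of omitting the criterion.** Controls at the base set; cases 5 points higher on each of the four criteria (45/35/30/55%). Under independence, cases have P(k ≥ 3) = 18.79% and P(k = 2) = 36.08%.
- Fifth omitted: 18.79 − 13.25 = 5.5 points.
- Glycaemic 40% v 25%: (18.79 + 0.40 × 36.08) − (13.25 + 0.25 × 32.75) = 33.2 − 21.4 = 11.8 points.
- Glycaemic 18.1% v 8.5%: 25.3 − 16.0 = 9.3 points.

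At ρ = 0.4 the three differences are 5.5, 9.3 and 7.8 points.

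**The case against.** The strongest reply is that the intention can be read from the plan. Section 1 speaks of dysglycaemia and of HbA1c as a MetS biomarker. Appendix 2 places fasting glucose from 5.6 mmol/L beside HbA1c from 5.7% as alternative routes to pre-diabetes, and 5.6 is also the MetS threshold. On that reading 39 mmol/mol is the natural cut-off, and setting 48 against it overstates the ambiguity. This supports 39 as the primary choice. It does not supply a rule, because neither appendix on HbA1c mentions MetS and the MetS text names only glucose.

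Three further points are fair.
- Most subjects (67–78% on the base assumptions) are classified without the fifth item. The prevalence still cannot be computed, only bounded.
- The sizes are driven by assumption. The 15-point glycaemic gap in step 7 has no source in the documents. With the pilot's gap the five-criterion difference falls to 7.8–9.3 points, and with a 5-point gap (30% v 25%) to 6.5–8.2, against 5.5 with the criterion omitted. Nor does the plan propose omission.
- The parameter lists in 8.1.3 and 10.3 contain no blood analytes at all, so the absence of glucose there proves little. The evidence is the panel and the letter in 8.3.

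**Conclusion.** The concern holds. The mismatch between the MetS rule and the data collected is certain and needs no assumption: subjects with exactly 2 of the other 4 criteria have no MetS status under the stated rule, so one of the four main endpoints cannot be computed as written.

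How many subjects this touches is not known from the documents. Under the assumed component rates it is roughly a fifth to a third of the sample, and the choice between the plan's two HbA1c cut-offs changes the class of about 2% to 12%. Known DM was ignored in these figures; counting it as positive would lower the cut-off effect slightly. The conclusion rests on the missing scoring rule, not on these sizes.

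**What to change.** Before analysis, reconcile sections 1, 8.3 and 10 with Appendix 4. For endpoint scoring only, replace the glucose criterion in section 10 and Appendix 4 with one based on collected data, for example HbA1c at or above 39 mmol/mol (the plan's own preDM cut-off) or a known diagnosis of DM, and call the result a modified NCEP ATP III definition. Report as sensitivity analyses (a) the 48 mmol/mol cut-off and (b) the bounds obtained by scoring all subjects with exactly 2 of the other 4 criteria as negative, then all as positive.

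In the same rewrite, make section 10 and Appendix 4 agree on HDL-C. The appendix counts drug treatment for reduced HDL-C and section 10 does not.

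For the glycaemic item the cost is wording only, since HbA1c and diagnosis of DM are already collected. The HDL-C clause needs a check that a matching treatment variable is recorded: section 10.3 names treatment for ASCVD and for hypercholesterolaemia, but not for reduced HDL-C.

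There are three drawbacks to state. HbA1c and fasting glucose need not classify the same people, so comparability with the cited definition falls. Section 8.3 itself says that ethnicity influences HbA1c. MetS would also share its glycaemic marker with the (pre)DM endpoint.
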